**1. SUMMARY**

In the 21st century, children are born into an obesity prone environment where consumption of nutrient-deplete and calorie-dense diets and sedentary behaviors are the norm. Mothers (and fathers) are more likely to be obese prior to conception and parental health at conception, particularly obesity, is linearly associated with obesity in children. Independent of obesity prior to pregnancy, excessive weight gain throughout pregnancy leads to higher adiposity in infancy. There are very few studies that have attempted to understand the role of the intrauterine environment and the impact of early life exposures on development of adiposity in humans. Understanding the amount and type of adipose tissue present early in life is important to understand how obesity develops in childhood and determines metabolic risk throughout one’s lifetime. We have been successfully deploying methodology in infant subjects at Pennington Biomedical to quantify measurements of energy metabolism and eating behavior. Our current measures of body composition include an indirect method of adiposity from a measurement of body volume using air displacement plethysmography. We are seeking to expand our methodological capability with direct measurements of adiposity including the quantification of both white and brown adipose tissues using dual energy x-ray absorptiometry and magnetic resonance imaging, respectively. The aim of this study therefore is to use state-of-the-art equipment and established methods supported by appropriate validation studies to develop methods at Pennington Biomedical that assess whole body adiposity (fat mass) and brown adipose tissue in infant subjects. This study will obtain important data pertaining to the accuracy and precision of the procedures and methods that is required to inform the development of future studies including these parameters as endpoints.

**2. STUDY AIMS**

The overarching goal of this study is to develop a technique for measuring whole body adiposity (fat mass) and supraclavicular brown adipose tissue in infant subjects. To this end the study will:

1. Develop a protocol for measurement of whole body adiposity in infant subjects using dual energy x-ray absorptiometry (DXA).
2. Develop a protocol for measurement of brown adipose tissue in infant subjects using a published, non-invasive measurement by magnetic resonance imaging.
3. Evaluate the accuracy and precision of the measurement of brown adipose tissue as well as feasibility of protocol completion in infant subjects measured twice within 1 to 10 days apart.

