neuroendocrine functioning and energy expenditure in the developing fetus [29-31]. Therefore understanding the physiological regulation of BAT is thus important for developing strategies to prevent or treat obesity and metabolic diseases and quantification of BAT from early in life is an important area of research.

In adults, PET/CT has been utilized due to its ability to measure active BAT metabolism in combination with radiotracer uptake. PET/CT however, is not suitable for research in infants. Several groups [32-34] have developed and validated protocols for the measurement of BAT in infant subjects using magnetic resonance imaging (MRI), which is non-invasive and presents minimal risk to infant subjects. In collaboration with [name], we will develop and optimize a MRI technique to quantitatively measure BAT mass in human infants at Pennington Biomedical.

As part of a translational research project funded by Pennington Biomedical, the aim of the study is to establish a technique for measuring whole body adiposity (fat mass) and supraclavicular brown adipose tissue in infant subjects using DXA and MRI, respectively.

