**TABLE 1. Schedule of Procedures**

Visit Assessment*	Visit 1 (14-28 days)	Visit 2 ( 1-10 days after Visit 1)
Informed Consent (Minor)	X	
Recumbent Length	X	X
Weight	X	X
PEA POD	X	
DXA	X	
MRI	X	X
Questionnaires#	X	
#Completed by a parent or legal guardian that signs the study informed consent and HIPAA authorization and accompanies the infant to the visit		

### 8.1. Visit 1

The parent/guardian and infant will be escorted to the Maternal and Infant Phenotyping Room for informed consenting. The minor informed consent form and HIPAA authorization will be provided for review and completion after all questions are answered. After obtaining written parental informed consent for participation, the following procedures will be performed: infant weight, recumbent length, body composition by PEA POD, DXA and MRI. Questionnaires will be administered to a parent/guardian who attends the visit. The DXA and MRI procedures will be completed while the infant is sleeping. The order of the procedures at the visit will be conducted in a manner that is most respectful to the schedule and temperament of the infant. For example, if the infant arrives at Pennington Biomedical and is soundly sleeping, once the parents/legal guardians sign the informed consent, the infant may proceed directly to imaging for DXA and MRI. Visit 2 will be scheduled to occur 1-10 days later.

### 8.2. Visit 2

The following procedures will be performed: infant weight, recumbent length, and MRI. The order of the procedures at the visit will be conducted in a manner that is most respectful to the schedule and temperament of the infant. Infants will be fed and calmed before preparation for MRI. The MRI procedures will be completed while the infant is sleeping.

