### **11.2. Data Analysis Plan**

As noted in Section 2. Aims, the primary aim is to develop techniques for measuring whole body adiposity (fat mass) and brown adipose tissue in infant subjects. We intend on understanding the repeat test accuracy of the measurement of infant BAT by calculating % BAT and comparing the test-retest reliability between Visit 1 and Visit 2 measurement within various equivalency intervals (e.g. within 15%, 10%, 5%). The coefficient of variation for the BAT measurement will be computed from the two measures performed under the same conditions 1 to 10 days apart.

% BAT will be calculated: 
$$\% BAT = \frac{BAT\ mass\ (by\ MRI)}{FAT\ mass\ (by\ DXA)}$$

Depending on the characteristics of the recruited cohort, exploratory analyses maybe undertaken to determine differences in measures between boys and girls, if energy expenditure is different on the account of maternal BMI, birth weight, breast milk versus formula-fed infants.

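### Aim 3 and the Summary promise accuracy and precision for brown adipose tissue (BAT), but section 11.2 can give only between-visit test-retest variability, which includes any true change over 1-10 days

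*Combined protocol and SAP*

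**What the plan says.** Section 2, Aim 3, commits the study to "Evaluate the accuracy and precision of the measurement of brown adipose tissue as well as feasibility of protocol completion in infant subjects", with each infant measured twice. Section 1 says more generally: "This study will obtain important data pertaining to the accuracy and precision of the procedures and methods".

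Section 11.2 turns this into an analysis. It opens with "We intend on understanding the repeat test accuracy of the measurement of infant BAT" and carries that out by calculating % BAT (BAT mass by MRI over fat mass by DXA) and "comparing the test-retest reliability between Visit 1 and Visit 2 measurement within various equivalency intervals", with 15%, 10% and 5% as examples. The CV is to be "computed from the two measures performed under the same conditions 1 to 10 days apart". The only other analyses are optional subgroup comparisons.

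On what is measured, section 8.1 lists weight, length, "body composition by PEA POD, DXA and MRI" at Visit 1. Section 8.2 lists weight, length and MRI at Visit 2. Neither visit includes a second method for BAT, and section 3 states that "PET/CT however, is not suitable for research in infants". Section 9.3.1.2 allows a rescan only to replace an unsatisfactory one, so no same-session repeat is planned. Section 11.1 says the data will feed later sample size estimates.

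**The concern.** Accuracy means closeness to a true or reference value. Precision means the scatter of repeated measurements of an unchanged quantity. The planned comparison gives neither in pure form. It gives the variability between two scans some days apart in young infants, without separating scanner and reading error from true change.

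Two consequences follow. Good agreement between visits could be reported as evidence of accuracy, which it is not. And if the CV is carried into a later sample size calculation as measurement error, it will on average be too large to the extent that BAT truly changes between visits.

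**Working it through.** The plan states no target CV, power or calculated sample size, so there is no figure of its own to reproduce. BAT values and rates of change below are assumptions; the documents give none.

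**1. Can the planned statistics detect bias?** For two readings a and b, within-infant CV = |a − b| / √2 / mean, and relative difference = |a − b| / mean.

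- Readings 100 and 112: mean 106, difference 12. CV = 12 / 1.414 / 106 = 8.0%; relative difference = 12 / 106 = 11.3%.
- The same scans read 50% high, 150 and 168: mean 159, difference 18. CV = 18 / 1.414 / 159 = 8.0%; relative difference = 18 / 159 = 11.3%.

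A constant proportional bias cancels. In a simulation with a true CV of 5%, scans reading 20% low, unbiased and 30% high all gave a within-infant CV of 5.0%. The DXA denominator does not help: DXA is done at Visit 1 only, and if that fat mass is used for both visits it cancels too.

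**2. What does the CV contain?** Let s be the measurement CV and d a true change, in % of the mean, common to all infants. The difference between visits then has mean d and variance 2s². The root-mean-square between-visit CV is √(s² + d²/2). For s = 5 and d = 10 it is √(25 + 50) = 8.7%.

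| Measurement CV | d = 0 | d = 5% | d = 10% |
|---|---|---|---|
| 3% | 3.0% | 4.6% | 7.7% |
| 5% | 5.0% | 6.1% | 8.7% |
| 8% | 8.0% | 8.7% | 10.7% |

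At s = 5% the variance is multiplied by 1, 1.5 and 3.0. With normally distributed differences, the share of pairs within 10% (relative) is 84%, 74% and 50%.

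**3. How precise is the CV from 10 infants?** With 10 pairs and no mean change, the 95% limits are the estimate times √(10/χ²), using the 97.5% and 2.5% points of χ² on 10 degrees of freedom. The factors are 0.70 and 1.75. With the mean change removed (9 degrees of freedom) they are 0.69 and 1.83. An estimate of 5.0% therefore has limits of about 3.5% and 8.8%.

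**4. Feasibility.** Aim 3 names it, but sections 11.1 and 11.2 give no completion measure or denominator. Section 5.3 excludes infants unable to complete two visits, section 10.3 provides for aborting a scan after three attempts, and section 12 provides payment for those who complete only Visit 1. The counts will therefore exist, but who belongs in the denominator is not stated.

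**The case against.** The strongest reply is that this is mainly one wrong noun. Aim 3 itself says the infants are measured twice, and section 11.2 describes the comparison as test-retest, so a careful reader can see what will be done. Sections 1 and 3 refer to earlier validation work. This is an unpowered pilot that section 11.1 does not expect to be published. The inflation of the CV rests on assumed change, which could be near zero at a one-day gap. It also errs towards larger later samples, and 10 pairs would mostly not resolve it: the limits around 5.0% contain both 6.1% and 8.7%.

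Much of that stands. It limits the size of the problem but does not remove it. Aim 3 says accuracy is evaluated in this study, and section 11.1 gives the data a later use that depends on the right label.

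Some stronger readings are tempting and are not supported:

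- **The CV will be materially inflated.** The documents give no rate of BAT change, so only the direction is known.
- **The 15/10/5% intervals might be percentage points of % BAT.** Beside a CV, relative differences are the natural reading; one clarifying phrase settles it.
- **Feasibility cannot be assessed.** The information arises from the procedures, and a simple count with a denominator supplies what is missing.
- **A DXA versus PEA POD comparison is a missing accuracy analysis.** No aim promises one, and it would say nothing about BAT.

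**Conclusion.** The mismatch between aim and analysis is real. Accuracy of BAT by MRI cannot be estimated from the scheduled data, whatever the results. This conclusion rests on the schedule and section 11.2 alone and needs no assumed number. The planned CV is between-visit variability, which equals measurement error only if BAT does not change between scans. How far they differ is unknown: under the assumptions shown, a measurement CV of 5% appears as anything from 5.0% to 8.7%. The pilot status excuses the small sample, but not an aim that the analysis cannot meet. The wording should be corrected. The interval definition and the feasibility count are minor clarifications.

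**What to change.** - **Aim 3 and section 11.2:** replace both *accuracy* and *precision* of BAT with *between-visit (1-10 day) test-retest variability*. State that this includes true biological change and that accuracy against a reference is not assessed.
- **Summary:** limit the sentence on what the data will show to test-retest variability of BAT by MRI, and drop the accuracy claim.
- **Section 11.2, reporting:** give with the CV its 95% confidence interval, the mean signed Visit 2 minus Visit 1 difference, and each infant's days between scans. State that a CV carried into later sample size estimates is between-visit variability, not pure measurement error.
- **Minor clarifications in section 11.2:** define the 15/10/5% intervals as relative differences, |V2 − V1| divided by the mean of the two. Report feasibility as the number of all consented infants with usable DXA, with usable MRI at both visits, and with all three, keeping missed visits and aborted scans in the denominator.

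The cost is wording and a few descriptive lines on data already collected, with no added procedure. The downside is that the study no longer claims to assess BAT accuracy. The signed mean shows only change common to all infants and cannot separate each infant's own change from measurement error.

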**3. BACKGROUND AND SIGNIFICANCE**

One of the most troubling aspects of the current epidemic of obesity is the increasing prevalence of obesity and type 2 diabetes among children [1, 2]. Childhood obesity is a very serious problem because adiposity can be traced between childhood and adulthood [3], and children with one or two obese parents are at a higher risk of weight gain during childhood and adolescence than children with both parents normal weight [4]. Furthermore, duration of obesity is an independent predictor of health outcomes [5]. The lifelong risk of obesity is now believed to begin in the womb. Children born to mothers who enter pregnancy overweight or obese have

significantly more adiposity at birth [6, 7], and longitudinal studies indicate that maternal adiposity has a positive influence on adiposity in offspring at 1 [8], 2 [9], 9 [10], and even 30 [11] years later.

Reliable measurements of adipose tissue from early life are critical to further knowledge regarding the development of obesity in humans. While non-invasive methods exist for measurement of body composition in infant subjects, these methods provide an indirect measurement of body fat and current equipment limit continued evaluation across childhood. For example, the PEA POD, which we frequently use at Pennington Biomedical uses air displacement technology which provides a measure of body volume. From a volume measurement, old equations are used to determine body density, and from and in conjunction with weight, fat mass and fat-free mass are assumed. The current devices for measurement of body volume in children are limited to birth – 6 months with the PEA POD and ~5 years of age and older with the BODPOD. Therefore, considerable and thought to be important data on body composition from 6 months to 4 years of age is not possible with this technique.

Dual energy x-ray absorptiometry (DXA) provides a direct measurement of body composition in three compartments; bone, fat and lean and is not limited to the age of the test subject. DXA is the gold standard methodology however the exposure to radiation emitted during the scan is a potential concern, particularly in vulnerable subjects. There are increasing numbers of reports of measurements of body composition in infants using DXA in the literature[12-23], including numerous studies that use DXA as a validation against other devices[17, 19, 20] and that describe best practices[13, 17, 18, 21]. Furthermore, while several studies use DXA to undertake cross-sectional comparisons of infant body composition across various groups[12, 22, 23], there are also prospective studies in infants to show changes in body composition across infancy[14-16]. The more widespread use of DXA in healthy populations demonstrates increased acceptability of DXA in infant subjects.

Not all adipose tissue is equal. For example, we know that the deposit of lipid in different regions of the body yields varying risks for metabolic disease. Furthermore, the morphology of adipose tissue also renders different metabolic functions. The most abundant adipose tissue and primary store of lipid is white adipose tissue. Brown adipose tissue (BAT) on the other hand is specialized for energy expenditure by dissipating energy as heat. BAT is able to convert nutrient-derived chemical energy into heat. The thermogenic capacity of BAT is due to its high content of mitochondria and expression of uncoupling protein 1 (UCP1), which dissipates the mitochondrial proton gradient as heat [24]. In rodents and human infants, BAT-mediated heat production is important for maintenance of normal body temperature in newborns after birth [24]. Recent studies in animals and humans further indicate that BAT plays a crucial role in the regulation of body weight and insulin sensitivity. While mice with impaired BAT thermogenesis are more susceptible to diet-induced obesity, BAT activation reduces dietary and genetic obesity [25, 26]. Moreover, the ability of BAT to take up high amounts of lipids and glucose from the blood alleviates hyperlipidemia and hyperglycemia [25, 26]. Although human BAT diminishes with age, metabolically active BAT persists into adulthood. Cold-induced activation of human BAT, as determined by F-FDG uptake using PET/CT, is closely associated with an increase in energy expenditure and a concomitant decrease in body fat mass [27, 28]. Moreover, BAT mass and activity are inversely correlated with BMI and body fat mass [27, 28], indicating that decreased BAT mass and activity may be implicated in the development of obesity and metabolic disorders.

The prevalence of childhood obesity is increasing worldwide. A number of human epidemiological studies and animal models link maternal obesity during pregnancy with an increased risk of obesity in offspring [29-31]. However, the underlying mechanisms by which maternal physiology predisposes offspring to obesity are not fully understood. Growing evidence suggests that the intrauterine nutritional and hormonal environments play a crucial role in metabolic programming of offspring obesity by permanently altering appetite control,

neuroendocrine functioning and energy expenditure in the developing fetus [29-31]. Therefore understanding the physiological regulation of BAT is thus important for developing strategies to prevent or treat obesity and metabolic diseases and quantification of BAT from early in life is an important area of research.

In adults, PET/CT has been utilized due to its ability to measure active BAT metabolism in combination with radiotracer uptake. PET/CT however, is not suitable for research in infants. Several groups [32-34] have developed and validated protocols for the measurement of BAT in infant subjects using magnetic resonance imaging (MRI), which is non-invasive and presents minimal risk to infant subjects. In collaboration with [name], we will develop and optimize a MRI technique to quantitatively measure BAT mass in human infants at Pennington Biomedical.

As part of a translational research project funded by Pennington Biomedical, the aim of the study is to establish a technique for measuring whole body adiposity (fat mass) and supraclavicular brown adipose tissue in infant subjects using DXA and MRI, respectively.

#### **4. RESEARCH DESIGN**

This is an observational method development study. Up to 10 infants will be enrolled in this study which includes two study visits to be completed within 1-10 days apart.

#### **5. STUDY POPULATION**

##### **5.1. Participants**

Up to 10 healthy, full-term infants aged 14 to 28 days old at enrollment with no contraindications to MRI will be recruited by Pennington Biomedical Research Center to participate in this study.

##### **5.2. Eligibility Criteria**

- Healthy, full-term infant
- Aged 14 to 28 days at Visit 1
- Willingness of parents to be notified of incidental findings from study procedures

##### **5.3. Exclusion Criteria**

- Born preterm (< 37 weeks gestation)
- Implanted metal or electronic objects that render MRI unsafe
- Unable to complete 2 clinic visits 1-10 days apart at Pennington Biomedical Research Center

#### **6. RECRUITMENT**

Parents of potential study participants will be recruited from within PBRC and the Greater Baton Rouge area via Institutional Review Board (IRB) approved posters and flyers and advertisements posted on the PBRC website (<http://www.pbrc.edu/clinicaltrials>) and through PBRC approved social media outlets including but not limited to Facebook, Twitter, blogs, and Craigslist. There is also the possibility to recruit parents of potential study participants who have participated in previous or current studies conducted at PBRC. Physician referrals from local midwives, obstetricians or pediatricians will also be used in recruitment efforts.

#### **7. SCREENING**

Interested parents or legal guardians will respond to targeted recruitment materials and will be directed to PBRC for initial screening via phone or email. Following initial contact by interested parents/legal guardians, a brief interview (via phone) will be conducted to describe the study and determine basic eligibility criteria. If the infant

has been born, basic eligibility criteria will be obtained through the initial screening survey for the infant who would potentially qualify to participate in the study. If the infant has not been born but is expected, basic contact information for the parent or legal guardian will be obtained so that they can be re-contacted about their interest after the infant is born. After the infant is born, the initial screening questions will be obtained to determine eligibility. Potential infants that do not meet criteria will be excluded. All eligible participants will be assigned a unique study ID number and referred to study staff for further screening. Email may be used for initial contact and other correspondence (e.g. study description, scheduling), but no protected health information will be contained in email correspondence.

## 8. ASSESSMENT SCHEDULE AND PROCEDURES

The first study visit will be completed when the infant reaches 2 – 4 weeks (14 - 28 days) of age. Study visits will be scheduled according to the ability of the parent/legal guardian to attend the second visit within 1 to 10 days after Visit 1 is completed. Before initiation of the first study visit (Visit 1), the study and study procedures will be explained to parents/legal guardians, and informed consent and HIPAA authorization will be obtained. An outline of the study visits and procedures to be performed is summarized in the Table 1.

